### 2.1.3 Dose-Limiting Toxicities

The DLT observation period is 15 days from date of first (W1D1) CMP-001 injection (i.e., following 3 doses of CMP-001; W1D1, W2D1, W3D1). Subjects who have received at least one dose of CMP-001 and pembrolizumab are evaluable for DLT assessments.

DLTs are defined below and only include AEs that are considered possibly, probably, or definitely related to the CMP-001 plus pembrolizumab combination. Attribution of AEs specifically to either CMP-001 or pembrolizumab is challenging, therefore, the relationship to CMP-001 should be based on attribution to the combination of the two study drugs (CMP-001 + pembrolizumab).

The following AEs will be considered DLTs **if deemed related to study drug combination**:

- Hematologic
  - Grade 4 neutropenia
  - Febrile neutropenia, defined as absolute neutrophil count (ANC) <1000/mm^3 with a temperature of  $\geq 38.3$  degrees C
  - Grade  $\geq 3$  neutropenic infection
  - Grade  $\geq 3$  thrombocytopenia with clinically significant bleeding seeking medical intervention
  - Grade 4 thrombocytopenia
- Non-hematologic:
  - Grade  $\geq 3$  toxicities (non-laboratory); excluding:
    - Grade 3 fatigue lasting <7 days
    - Grade 3 arthralgia or myalgia that downgrades to less or equal to grade 2 within 3 days of supportive care
    - Grade 3 pain at injection site that downgrades to less than or equal to Grade 2 within 3 days of supportive care

- Grade 3 electrolyte abnormalities that are asymptomatic and reversed with medical intervention within 3 days
  - Grade  $\geq 3$  nausea, vomiting or diarrhea despite maximal medical intervention
  - Grade 4 aspartate aminotransferase (AST) and alanine aminotransferase (ALT) unless alternate explanations such as viral hepatitis or disease progression in the liver
- Other (non- AST/ALT) non-hematologic Grade  $\geq 3$  laboratory value if the abnormality leads to overnight hospitalization

[figure not shown]
[figure not shown]

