**IMPORTANT:** CMP-001 activates plasmacytoid dendritic cells (pDC) through agonism of TLR9. Upon activation by CMP-001, pDCs will induce large amounts of interferon and TH1-promoting cytokines. Therefore, it is expected that toxicities associated with CMP-001 dosing may resemble interferon-related toxicities as well as symptoms associated with cytokine release such as chills, rigors, fever, nausea/vomiting, flu-like symptoms and/or hypotension which may present hours after CMP-001 injection. **Therefore, AEs such as headache, chills, rigors, fever, nausea/vomiting, flu-like symptoms and/or hypotension that are Grade 3 and below AND resolved to Grade 1 or below within 24 hours with standard supportive care will not be considered a DLT.** All toxicities regardless of grade should be managed according to standards of care and reported as AEs.

An AE believed by the Investigator to be caused by tumor flare or pseudoprogression does not necessarily need to be considered a DLT. Any such cases that would otherwise meet DLT criteria must be discussed immediately with the Medical Monitor. If the Investigator, Medical Monitor, and Sponsor agree that tumor flare is a likely explanation for the AE, treatment with CMP-001 may continue as long as the subject is closely monitored by the Investigator or study staff while on study.

Subjects who experience a DLT will have CMP-001 and pembrolizumab dosing withheld until the toxicity has returned to  $\leq$  Grade 1. If the Investigator determines that continued treatment with CMP-001 is in the subject's best interest, treatment of CMP-001 may resume at a reduced dose, one dose level lower than the subject's current dose at the same schedule after consultation with the Sponsor. Only one dose reduction is allowed. Subjects who continue to experience DLTs must come off study. If a CMP-001 injection is delayed due to toxicity, including a DLT, it should be given as soon as possible once the toxicity has resolved.

The Investigator may escalate the subject back to the original dose level if: 1) the lower dose level was tolerated without any DLTs; 2) Sponsor approval is given.

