Pneumonitis	Grade 2	Withhold	
 
• Administer corticosteroids (initial dose of 1 to 2 mg/kg prednisone or equivalent) followed by taper
 
	
 
• Monitor participants for signs and symptoms of pneumonitis
 
• Evaluate participants with suspected pneumonitis with radiographic imaging and initiate corticosteroid treatment
 

	Recurrent Grade 2, Grade 3 or 4	Permanently discontinue	
 
• Add prophylactic antibiotics for opportunistic infections
 
	
Diarrhea/Colitis	Grade 2 or 3	Withhold	
 
• Administer corticosteroids (initial dose of 1 to 2 mg/kg prednisone or equivalent) followed by taper
 
	
 
• Monitor participants for signs and symptoms of enterocolitis (ie, diarrhea, abdominal pain, blood or mucus in stool with or without fever) and of bowel perforation (ie, peritoneal signs and ileus)
 
• Participants with <math>\geq</math>Grade 2 diarrhea suspecting colitis should consider GI consultation and performing endoscopy to rule out colitis
 
• Participants with diarrhea/colitis should be advised to drink liberal quantities of clear fluids. If sufficient oral fluid intake is not feasible, fluid and electrolytes should be substituted via IV infusion
 

	Recurrent Grade 3 or Grade 4	Permanently discontinue		

irAEs	Toxicity Grade (CTCAE v5.0)	Action With Pembrolizumab	Corticosteroid and/or Other Therapies	Monitoring and Follow-up
AST or ALT Elevation or Increased Bilirubin	Grade 2 a	Withhold	
 
Administer corticosteroids (initial dose of 0.5 to 1 mg/kg prednisone or equivalent) followed by taper
 
	
 
Monitor with liver function tests (consider weekly or more frequently until liver enzyme value returned to baseline or is stable)
 

	Grade 3 b or 4 c	Permanently discontinue	
 
Administer corticosteroids (initial dose of 1 to 2 mg/kg prednisone or equivalent) followed by taper
 
	

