	Grade 2, 3 or 4	Permanently discontinue		
Exfoliative Dermatologic Conditions	Suspected SJS, TEN, or DRESS	Withhold	
 
Based on severity of AE administer corticosteroids
 
	
 
Ensure adequate evaluation to confirm etiology or exclude other causes
 

	Confirmed SJS, TEN, or DRESS	Permanently discontinue		
All Other irAEs	Persistent Grade 2	Withhold	
 
Based on severity of AE administer corticosteroids
 
	
 
Ensure adequate evaluation to confirm etiology or exclude other causes
 

	Grade 3	Withhold or discontinue based on the event e		
	Recurrent Grade 3 or Grade 4	Permanently discontinue		

irAEs	Toxicity Grade (CTCAE v5.0)	Action With Pembrolizumab	Corticosteroid and/or Other Therapies	Monitoring and Follow-up

AE(s)=adverse event(s); ALT= alanine aminotransferase; AST=aspartate aminotransferase; CTCAE=Common Terminology Criteria for Adverse Events; DRESS=Drug Rash with Eosinophilia and Systemic Symptom; GI=gastrointestinal; IO=immuno-oncology; ir=immune related; IV=intravenous; SJS=Stevens-Johnson Syndrome; T1DM=type 1 diabetes mellitus; TEN=Toxic Epidermal Necrolysis; ULN=upper limit of normal.
 
Note: Non-irAE will be managed as appropriate, following clinical practice recommendations.
 
a AST/ALT: >3.0 to 5.0 x ULN if baseline normal; >3.0 to 5.0 x baseline, if baseline abnormal; bilirubin:>1.5 to 3.0 x ULN if baseline normal; >1.5 to 3.0 x baseline if baseline abnormal
 
b AST/ALT: >5.0 to 20.0 x ULN, if baseline normal; >5.0 to 20.0 x baseline, if baseline abnormal; bilirubin:>3.0 to 10.0 x ULN if baseline normal; >3.0 to 10.0 x baseline if baseline abnormal
 
c AST/ALT: >20.0 x ULN, if baseline normal; >20.0 x baseline, if baseline abnormal; bilirubin: >10.0 x ULN if baseline normal; >10.0 x baseline if baseline abnormal
 
d The decision to withhold or permanently discontinue pembrolizumab is at the discretion of the investigator or treating physician. If control achieved or ≤ Grade 2, pembrolizumab may be resumed.
 
e Events that require discontinuation include, but are not limited to: encephalitis and other clinically important irAEs (eg, vasculitis and sclerosing cholangitis).
				

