**Table 8 Pembrolizumab Infusion Reaction Dose modification and Treatment Guidelines**

NCI CTCAE Grade	Treatment	Premedication at Subsequent Dosing
Grade 1 Mild reaction; infusion interruption not indicated; intervention not indicated	Increase monitoring of vital signs as medically indicated until the participant is deemed medically stable in the opinion of the investigator.	None
Grade 2 Requires therapy or infusion interruption but responds promptly to symptomatic treatment (e.g., antihistamines, NSAIDs, narcotics, IV fluids); prophylactic medications indicated for ≤24 hrs	Stop Infusion. Additional appropriate medical therapy may include but is not limited to: IV fluids Antihistamines NSAIDs Acetaminophen Narcotics Increase monitoring of vital signs as medically indicated until the participant is deemed medically stable in the opinion of the investigator. If symptoms resolve within 1 hour of stopping drug infusion, the infusion may be restarted at 50% of the original infusion rate (e.g. from 100 mL/hr to 50 mL/hr). Otherwise dosing will be held until symptoms resolve and the participant should be premedicated for the next scheduled dose. Participants who develop Grade 2 toxicity despite adequate premedication should be permanently discontinued from further study drug treatment	Participant may be premedicated 1.5h (± 30 minutes) prior to infusion of Pembrolizumab with: Diphenhydramine 50 mg po (or equivalent dose of antihistamine). Acetaminophen 500-1000 mg po (or equivalent dose of analgesic).
Grades 3 or 4 Grade 3: Prolonged (i.e., not rapidly responsive to symptomatic medication and/or brief interruption of infusion); recurrence of symptoms following initial improvement; hospitalization indicated for other clinical sequelae (e.g., renal impairment, pulmonary infiltrates) Grade 4: Life-threatening; pressor or ventilatory support indicated	Stop Infusion. Additional appropriate medical therapy may include but is not limited to: Epinephrine** IV fluids Antihistamines NSAIDs Acetaminophen Narcotics Oxygen Pressors Corticosteroids Increase monitoring of vital signs as medically indicated until the participant is deemed medically stable in the opinion of the investigator. Hospitalization may be indicated. **In cases of anaphylaxis, epinephrine should be used immediately. Participant is permanently discontinued from further study drug treatment.	No subsequent dosing

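### For dose-limiting toxicities (DLTs) that are also permanent-stop events in Tables 7 or 8, Section 2.1.3 gives pembrolizumab only a temporary hold, and no text says which rule governs each drug

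*Combined protocol and SAP*

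**What the plan says.** **Section 2.1.3.** After a DLT, "Subjects who experience a DLT will have CMP-001 and pembrolizumab dosing withheld until the toxicity has returned to" Grade 1 or below. If the investigator judges it to be in the subject's interest, and after consulting the sponsor, "treatment of CMP-001 may resume at a reduced dose, one dose level lower than the" subject's current one. That sentence names CMP-001 only. The only mandatory stop in the section is for repeated events: "Subjects who continue to experience DLTs must come off study".

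The DLT definition covers Grade 3 or higher "toxicities (non-laboratory); excluding" a short list that does not include pneumonitis, neurological toxicity, myocarditis or infusion reaction. It also covers "Grade 4 aspartate aminotransferase (AST) and alanine aminotransferase (ALT) unless alternate explanations such as viral hepatitis or disease progression in the liver". Relatedness is judged for the two-drug combination.

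**Section 6.2.2, Table 7.** The action column concerns pembrolizumab. The pneumonitis row for "Recurrent Grade 2, Grade 3 or 4" carries permanent discontinuation. So do Grade 3-4 neurological toxicity, Grade 2-4 myocarditis and Grade 3-4 AST/ALT. Grade 2-4 hypothyroidism carries an instruction to continue. General instruction 4 sets resumption at Grade 1 or below. Footnote d, attached to certain endocrine rows, says: "If control achieved or ≤ Grade 2, pembrolizumab may be resumed".

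**Section 6.2.2.1, Table 8.** For a Grade 3 or 4 infusion reaction: "Participant is permanently discontinued from further study drug treatment".

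**Sections 5.5 and 6.2.** Section 5.5 makes unacceptable events described in Section 6.2.2 a reason for mandatory discontinuation of study treatment. Section 6.2 expects both drugs to be stopped, temporarily or permanently, in most cases. It allows one drug to be handled separately if the toxicity is more clearly tied to it.

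**The concern.** A DLT is the event for which site staff most need one unambiguous instruction per drug. Section 2.1.3 reads as a complete rule: hold both drugs, wait for Grade 1, consider resuming CMP-001. Someone working from that section would treat a first Grade 3 pneumonitis as a temporary hold of pembrolizumab. Someone working from Table 7 would stop it for good. Both would be following the protocol, and nothing in either section sends the reader to the other. What is at stake is patient safety and consistent conduct between patients.

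**Working it through.** No arithmetic applies. I compared the DLT categories in Section 2.1.3 with the actions in Tables 7 and 8, separately for each drug, and then looked for an order of precedence in Sections 5.4.3, 5.5 and 6.2.

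| Event, if related to the combination | DLT under 2.1.3? | 2.1.3: pembrolizumab | 6.2.2: pembrolizumab | Result |
|---|---|---|---|---|
| Grade 3-4 pneumonitis | Yes, non-laboratory Grade 3 or higher | Hold until Grade 1 or below | Permanent stop | Conflict |
| Grade 3-4 neurological toxicity | Yes, same category | Hold | Permanent stop | Conflict |
| Grade 3-4 myocarditis | Yes, same category | Hold | Permanent stop | Conflict |
| Grade 4 AST/ALT | Yes, listed by name | Hold | Permanent stop | Conflict |
| Grade 3-4 infusion reaction | Yes, unless the 24-hour carve-out applies | Hold | Permanent stop (Table 8) | Conflict |
| Grade 3-4 hypothyroidism | Only if it counts as a non-laboratory toxicity | Hold | Continue | Conflict in the other direction |
| Grade 3-4 hypophysitis or hyperthyroidism | Same condition | Hold until Grade 1 or below | Withhold or stop; footnote d allows resumption on control or at Grade 2 or below | Resumption grades differ |

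**CMP-001 against Table 7.** There is no direct conflict. Table 7's action column is for pembrolizumab, so stopping pembrolizumab while CMP-001 resumes satisfies both texts.

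**CMP-001 against Table 8 and Section 5.5.** The scope is ambiguous. Table 8's title and section concern pembrolizumab, but its stop is worded for study drug, and Section 2.1.3 describes CMP-001 and pembrolizumab together as the two study drugs. Section 5.5 speaks of study treatment. If either term covers both agents, it conflicts with the option in Section 2.1.3 to resume CMP-001.

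**Limits of the overlap.**
- Hematologic DLTs have no dedicated row in Table 7.
- A first Grade 3 colitis is a hold in Table 7. Grade 3 events in the row for other immune-related events may be a hold or a stop.
- Grade 1-2 myocarditis is not a DLT.
- Nephritis that is only a laboratory abnormality is a DLT only if it leads to overnight hospitalization.
- Cytokine-type symptoms of Grade 3 or below that settle to Grade 1 or below within 24 hours are not DLTs. This removes part of the Table 8 overlap at Grade 3 and none at Grade 4.
- The DLT observation period is 15 days, while Section 6.2.2 notes that immune-related events may appear months later.

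**Ordering of severity.** Grade 3 AST/ALT is not a listed DLT but is a permanent stop in Table 7. Grade 4 AST/ALT is a DLT and, read from Section 2.1.3 alone, is a temporary hold. On that reading the milder event is handled more strictly.

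**Precedence.** None is stated. Section 5.4.3 applies the Table 7 guidance to events related to either drug, so Table 7 cannot be set aside by attributing an event to CMP-001. The one-drug exception in Section 6.2 depends on attribution to a single agent, which Section 2.1.3 calls challenging.

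**The case against.** The best defence is that the texts can be layered. The hold in Section 2.1.3 can be read as a minimum condition, with the event-specific rules of Section 6.2.2 added on top. Section 2.1.3 never says outright that pembrolizumab resumes, and its resumption of CMP-001 is optional. Section 5.5 ties a mandatory stop to Section 6.2.2, which leans towards that section. Footnote d is permissive, so waiting for Grade 1 complies with it as well as with general instruction 4 and Section 2.1.3. The Grade 1 versus Grade 2 difference is therefore largely internal to Table 7.

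Much of this stands, and it rules out the stronger reading that one patient is told both to resume and to stop. The explicit resumption covers CMP-001 only and is optional, and the Table 7 stop covers pembrolizumab only.

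Layering does not remove the problem, for three reasons. A hold with a stated end-point reads as temporary, and Section 2.1.3 gives no sign that another section overrides it. Section 5.5 does not say which rows of Section 6.2.2 count as unacceptable, and its reference to study treatment reopens the question of CMP-001. Nor can layering reconcile a hold with an instruction to continue, as for Grade 3-4 hypothyroidism if it counts as a DLT.

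**Conclusion.** The conflict is real but limited. It is clear for pembrolizumab in the DLTs that Tables 7 and 8 list for permanent discontinuation. For CMP-001 it depends on what study drug in Table 8 and study treatment in Section 5.5 cover. The hypothyroidism point assumes that the event counts as a DLT. The footnote d difference is secondary, because the footnote is permissive.

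The number of patients affected cannot be stated: the documents do not give the share of DLTs that fall under Tables 7 and 8.

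A reader might infer that the conflict lowers the response counts or the dose-selection probabilities. The documents do not support that. Patients stopped under Section 5.5 remain under monitoring, nothing makes them automatic non-responders, and Section 2.1.3 itself holds both drugs after a DLT. The operating characteristics in Section 9.2 and Appendix F are not shown to be affected. This is a safety-relevant contradiction in the text, not a sample-size or error-rate problem.

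**What to change.** Reconcile Sections 2.1.3, 5.5, 6.2 and 6.2.2 (Tables 7 and 8). In Section 2.1.3, for DLTs that are also listed in Table 7 or 8, state:
- which section governs pembrolizumab and which governs CMP-001;
- whether a Table 8 stop, and study treatment in Section 5.5, include CMP-001;
- which resumption grade applies, given Section 2.1.3, general instruction 4 and footnote d;
- how an event that Table 7 says to continue through is handled if it counts as a DLT.

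Then remove the conflicting wording and add cross-references both ways. The choice of clinical rule belongs to the sponsor and the investigator. The cost is protocol wording only; the DLT definition, sample size and BOIN12 decision tables need not change.

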**Table 1a: Dose Levels in the Adaptive Design**

Dose Level	Pembrolizumab Dose	CMP-001 Dose (mg)
1*	Per Product Label	7.5
2	Per Product Label	10

\* Starting dose

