- If the current dose level  $j$  is the lowest dose, treat the new patients at the lowest dose unless the RDS of the lowest dose is “E,” at which point terminate the trial.
- If the current dose level  $j$  is not the lowest dose and the RDS of dose level  $j - 1$  is not “E,” de-escalate the dose to level  $j - 1$  to treat the next cohort of patients.
- If the current dose level  $j$  is not the lowest dose and the RDS of dose level  $j - 1$  is “E,” stay at the current dose level  $j$  to treat the next cohort of patients unless the RDS of dose level  $j$  is “E,” at which point terminate the trial.

3. Repeat step 2 until the maximum sample size of 21 is reached or if the number of patients treated on any dose reaches 12. Then, use the isotonic estimation method described in Lin et al. (Lin et al., 2020) to select the (biologically optimal) dose that is admissible and that has the highest estimated utility.

**We have treated 6 patients on the study so far. The first 3 patients were treated at the dose level of 5 mg and the next 2 patients at dose level 7.5 mg. The three patients treated at 7.5 mg CMP001 dose will be included to the maximum accrual goal of 21 with this updated protocol. (Previous version had target accrual of 39 patients). This means additional 18 patients are needed to complete the study. Patients treated at 5 mg included 2 patients with recent anti-B cell therapy (Rituximab, CAR T cells) and did not develop antiQbeta antibody important for CMP001 function. We updated the exclusion criteria to account for this observation.**

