### 4.3 Justification for Dose

#### 4.3.1 Justification for CMP-001 dosing:

The first CMP-001 injection stimulates antibody formation to the VLP of CMP-001 and will be given subcutaneously. Subsequently, CMP-001 will be administered by intratumoral injection every week for seven doses. The seventh dose (C7D1) is to be followed by booster doses given every 3 weeks.

The starting dose for CMP-001, 5 mg, was selected based upon the combination with identical pembrolizumab dosing in a Phase I/II trial of the two agents in metastatic melanoma led at the University of Iowa (NCT02680184). In the first 2 cohorts in melanoma, no DLT was seen at the 5mg dose, while biologic activity and some toxicity was seen at the 7.5 mg dose.

The highest dose considered in that study, 20 mg, is the maximum planned for consideration in CMP-001 given the current formulation.

Rationale for weekly dosing of CMP-001 for the first seven doses is supported by the following points:

- The safety of weekly dosing of up to 5 mg is well-supported by previous clinical trials of CYT003-QbG10 in non-oncology indications.
- The efficacy of weekly dosing is supported by the observation that weekly vaccination of melanoma patients with the closely related compound CYT004 (essentially CYT003-QbG10 conjugated to a tumor antigen) rapidly induced anti-tumor CD4+ and CD8+ T cell responses in the majority of subjects (Braun et al., 2012; Goldinger et al., 2012; Speiser et al., 2010). Thus, considering intratumoral administration of CMP001 as a kind of in situ vaccination, weekly dosing is also expected to induce anti-tumor immunity.
- Within a week of the initial dose, humans produce an anti-Qb antibody response adequate to provide uptake of the second dose into the target TLR-9-responsive immune cells.
- The desired Th1-like pharmacodynamic effects of CpG ODN injection persist in the draining lymph nodes of mice for more than one week (Lipford, Sparwasser, Zimmermann, Heeg, & Wagner, 2000) after a single injection; less frequent dosing may fail to sustain the desired IFN induction in the tumor microenvironment and draining lymph nodes, allowing the immune suppressive effects of the tumor to dominate.

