**Table 5: CMP-001 Injection Volumes**

Dose Cohort	Volume to be injected for 1mg/mL Concentration	Volume to be Injected for 5 mg/mL concentration
7.5 mg	7.5 mL	1.5 mL
10 mg	10.0 mL	2 mL

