- i. Blood samples (20 ml) for research including exploratory biomarker, immunogenicity studies, and assessment of pharmacodynamics are to be collected at screening and then on following days and times:  
 Blood draw pre-treatment W1D1 or before, W3D1, W6D1, W10D1 prior to dosing with CMP-001 – Additional blood draw with subsequent cycles may be requested.
- j. Archival tumor samples should be identified at Screening, if available for potential access later. Additional tumor biopsies are optional and may be collected at other times then specified below at the discretion of the Investigator. Optional tumor biopsies (fresh frozen when feasible and typically FNA), will be collected prior to starting treatment on W1D1, W3D1, W6D1, W10D1. If pre-treatment biopsy prior to W1D1 treatment not done, it can be scheduled with W2D1 intra-tumor injection.
- k. In women of childbearing age, Urine pregnancy testing should be performed at Screening and prior to 1st CMP-001 injection (W1D1), prior to 4th CMP-001 injection (W4D1), prior to 7th CMP-001 injection (W7D1), followed by every 3 weeks prior to treatment and EOT. A negative test within 72 hours of treatment is acceptable.
- l. CT neck/chest/abdomen/pelvis with contrast or PET-CT scans to assess response will be at W7D1 (or after two cycles) and then as clinically indicated. Subjects may be asked to provide historical scans (scans performed prior to Screening) for informational purposes prior to starting CMP-001 therapy, if available.
- m. The first CMP-001 injection stimulates antibody formation to the VLP of CMP-001 and will be given subcutaneously. Subsequently, CMP-001 should be administered as close to the tumor as possible if intratumoral injection not possible. A window of  $\pm 2$  day is permitted for the CMP-001 dose schedule for the first weekly CMP-001 injections and a window of  $\pm 7$  days is permitted for every 3 week CMP-001 injections. To assure maximum effectiveness, consecutive IT injections of CMP-001 should always be administered at least 96 hours apart. No CMP-001 dose should be skipped. If a CMP-001 dose needs to be delayed due to toxicity the dose should be completed as soon as the toxicity has resolved.

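### The rule for resuming CMP-001 after a DLT cannot be applied at 7.5 mg, the starting and lowest dose level

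*Combined protocol and SAP*

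**What the plan says.** All references are to the combined protocol and SAP.

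- **Resumption (Section 2.1.3).** After a DLT both drugs are withheld until the toxicity is Grade 1 or lower. If the investigator judges it to be in the subject's interest, and after consulting the sponsor, CMP-001 "may resume at a reduced dose, one dose level lower than the" subject's current dose. One reduction is allowed. Subjects whose DLTs continue leave the study.
- **Return to the earlier dose (Section 2.1.3).** "The Investigator may escalate the subject back to the original dose level", provided that the lower level was tolerated without a DLT and the sponsor approves.
- **Delayed injections (Section 2.1.3).** Where an injection is delayed for toxicity, a DLT included, "it should be given as soon as possible once the toxicity has resolved". Flow chart footnote m adds: "No CMP-001 dose should be skipped". Neither sentence names a dose.
- **Levels available.** Table 1a ("Dose Levels in the Adaptive Design") lists 7.5 mg, marked as the starting dose, and 10 mg. Table 5 ("CMP-001 Injection Volumes") has rows for those two doses only.
- **Where 5 mg appears.** Section 2.1.2 gives it as history: "The first 3 patients were treated at the dose level of 5 mg". Section 4.3.1 still calls it the starting dose, which Table 1a contradicts, and says: "The safety of weekly dosing of up to 5 mg is well-supported by previous clinical trials"; those were trials in non-oncology indications.
- **Who is analysed (Sections 9.3 and 5.5).** The Safety and Efficacy Population requires at least one recorded post-baseline response assessment. Section 5.5 replaces early withdrawals only when the reason is not a DLT.

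**The concern.** The post-DLT rule defines a step from 10 mg to 7.5 mg and none from 7.5 mg. The re-escalation paragraph fails at 7.5 mg for the same reason, since its first condition is that a lower level was tolerated. What remains for a first DLT at 7.5 mg is an inference (no lower level, so no resumption) next to two instructions that the delayed injection be given. A safety rule that gives no answer at the starting dose, and has neighbouring text pulling the other way, is more than a missing detail. Patients with the same DLT could be stopped, or taken to 5 mg on the strength of its earlier use.

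A related gap affects both levels. A patient who has a DLT and never reaches a post-baseline scan falls outside the Section 9.3 population, yet is not replaced under Section 5.5. The plan does not say how such a patient enters the efficacy count.

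**Working it through.** **1. Applying the rule at each level**

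| Step in Section 2.1.3 | DLT at 10 mg | DLT at 7.5 mg |
|---|---|---|
| Withhold to Grade 1 or lower | applies | applies |
| Resume one level lower | 7.5 mg | no level in Table 1a |
| Volume for the reduced dose (Table 5) | 1.5 mL at 5 mg/mL | no row |
| Re-escalate after tolerating the lower level | 10 mg | condition cannot be met |
| Leave study if DLTs continue | applies | applies, but does not cover a first DLT |
| Give the delayed injection (Section 2.1.3, footnote m) | at 7.5 mg | dose not stated |

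**2. The plan's own figures.** Section 9.2 gives 15.6 expected patients and 85% total selection for the case that is scenario 5 of Table B. Table B gives 7.6 + 8.0 = 15.6 patients and 35.8% + 48.8% = 84.6%. Both agree.

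**3. How often the gap could still arise.** Section 2.1.2 reports six patients treated. It says in one sentence that two were at 7.5 mg and in the next that three were. Three is consistent with the total (3 at 5 mg + 3 = 6) and with the 18 still to enrol (21 − 18 = 3). Every simulated trial starts with three patients at 7.5 mg, so:

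expected further DLT patients at 7.5 mg = (Table B number at 7.5 mg − 3) × DLT rate

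- Scenario 5: (7.6 − 3) × 0.20 = 0.92
- Scenario 6: (8.7 − 3) × 0.20 = 1.14
- Scenario 8: (8.9 − 3) × 0.30 = 1.77
- Smallest, scenarios 1 and 2: (4.2 − 3) × 0.20 = 0.24
- Largest, scenario 12: (7.8 − 3) × 0.50 = 2.40

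With two treated instead of three, scenarios 5, 6 and 8 give 5.6 × 0.20 = 1.12, 6.7 × 0.20 = 1.34 and 6.9 × 0.30 = 2.07.

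If six more patients are treated at 7.5 mg, the chance of at least one DLT is 1 − 0.80^6 = 74% at a rate of 0.20 and 1 − 0.70^6 = 88% at 0.30.

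These figures average over the possible outcomes in the first three patients, which the documents do not report.

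**4. Volume of a 5 mg dose.** Section 10.1 gives a 5 mg/mL supply, which may be diluted to 1 mg/mL. So 5 mg is 5/5 = 1 mL or 5/1 = 5.0 mL, on the same basis as the existing Table 5 rows (7.5/5 = 1.5 mL; 10/5 = 2 mL).

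**The case against.** The best defence is that the text already yields a safe answer. The only route back after a DLT is a reduced dose, after sponsor consultation. Return to the original dose needs tolerance of a lower level and sponsor approval. The delayed-injection sentence and footnote m govern timing, and a general timing rule does not override the specific dose rule beside it. With no lower level, CMP-001 is simply not resumed. The trial is single-centre, so divergent handling is unlikely, and the sponsor knows 5 mg from earlier patients.

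Most of this stands, and it keeps the point minor. It does not close the gap: consultation is not a rule, stopping is never stated, and 5 mg is nowhere named as a reduction level.

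A reader might infer two stronger things.

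- **That the protocol permits re-challenge at 7.5 mg after a DLT there.** That is a strained reading, for the reasons just given. The fair statement is that the text does not expressly exclude it.
- **That the gap tilts selection between 7.5 mg and 10 mg.** The documents cannot support this. They give no response rate after a DLT, the decision boundaries are not visible in the available text, and the scan that supplies the efficacy count is not fixed. Section 6.2 also allows toxicity to stop both drugs at either level. Any shift would rest on stacked assumptions. It would not measure what a repair recovers either: the response rate at 5 mg is unknown, and a permanent stop at 7.5 mg would preserve the difference between levels.

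It can also be said that the Section 9.3 question is separate, since it arises at 10 mg too. That is correct, and it is raised here as a separate amendment.

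**Conclusion.** The concern holds as a minor defect in a safety rule. That the rule has no target at 7.5 mg follows directly from Section 2.1.3 with Tables 1a and 5 and needs no assumption. The exposure figures rest on Table B's true-rate scenarios and on three 7.5 mg patients already treated: about one to two further DLT patients in scenarios 5, 6 and 8. They are upper limits on those affected, because the investigator may choose not to resume at all. The BOIN12 decision rules and the Table B figures are unaffected.

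The population gap in Section 9.3 holds on its own, at both dose levels. The documents give no basis for estimating how many DLT patients will lack a scan.

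**What to change.** **Section 2.1.3.** Choose one rule and write it down:

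- A subject with a DLT at 7.5 mg may resume once, at 5 mg. This dose is for reduction only and is not open to cohort assignment. Add a 5 mg row to Table 5: 5.0 mL at 1 mg/mL, 1 mL at 5 mg/mL.
- Or, if 5 mg is judged unsuitable, a subject with a DLT at 7.5 mg permanently stops CMP-001.

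Under either rule, add that CMP-001 is not resumed directly at the dose that caused the DLT, and that any delayed injection follows the reduction rule. The re-escalation paragraph can stay.

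**Footnote m.** Limit the instruction against skipping doses so that it matches the amended Section 2.1.3.

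**Section 9.3, with Section 2.1.2 to match.** At both levels, keep a subject with a DLT and no post-baseline scan in the population, and count that subject as a non-response at the assigned level.

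**Cost.** A few sentences, a footnote edit and, under the first option, one table row; no added patients. Under that option a few patients may receive 5 mg, for which the documents give no response rate. The counting rule may lower the reported response rate slightly.
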